3.6.4. Date(s): April 2012-April 2018

3.6.5. Source of Research Material:

Source of Research Material per Participant (Procedures)	# Routine Care	# Research Driven	# Total Procedures
Group 1 Only: 1 gram (2-500 mg capsules) water-soluble cinnamon extract (Cinnulin PF) (once a day for 1 year)	0	1 year	1 year
Group 2 Only: 2 placebo pills (once a day for 1 year)	0	1 year	1 year
Fasting glucose	0	3	3
Fasting comprehensive metabolic panel	3	3	6
Hemoglobin A1C	4	5	9
ECG	0	2	2
Lipid panel	4	5	9
Study Medication Diary	0	4	4
RAND 36-Item Health Questionnaire	0	3	3

"All specimens collected at Nellis AFB will be kept at Nellis AFB and handled and disposed of in accordance with federal regulations."

3.6.6. Subjects:

We will recruit male and female subjects Nellis AFB between the ages of 18-65 years with a diagnosis of pre-diabetes. Eligible subjects will be recruited from any form and any stage of "standard" lifestyle intervention for pre-diabetes at an individual base. "Standard" lifestyle intervention for pre-diabetes could include Group Lifestyle Balance (GLB), nutrition classes, Better Body/Better Life, or anything an investigator certifies as standard practice at that base. No special populations (i.e. children, prisoners, pregnant women, mentally disabled persons, or economically or educationally disadvantaged persons) will be eligible for this study. There are currently 2,950 diabetic patients empaneled for care at Nellis AFB. Several thousand more are pre-diabetic--many of these will likely attain the diagnosis of diabetes within 36 months.

3.6.7. Inclusion/Exclusion Criteria:

Inclusion:

- Patients will be Nellis AFB DoD beneficiaries between the ages of 18-65 years.
- Diagnosis of pre-diabetes (defined as a fasting plasma glucose (FPG) 100-125mg/dl or hemoglobin A1C 5.7-6.4% or a 2-hour oral glucose tolerance test (OGTT) 140-199).

Exclusion:

- Patients who are less than 18 yrs of age or greater than 65 years of age
- Patients who are known to have or develop during the study any of the following upon review of their medical record:
 - o Diabetes Mellitus (defined as fasting plasma glucose (FPG) ≥126mg/dl, hemoglobin A1C ≥6.5%, or a 2-hour oral glucose tolerance test (OGTT) ≥200mg/dl)

- o Stage 3 kidney disease or worse
- o Renal insufficiency defined as a glomerular filtration rate (gfr) of less than 60ml
- o Celiac disease
- o Insulinoma
- o Cushing's disease
- o Hyperthyroidism
- o Acromegaly
- o Pheochromocytoma
- o Addison's disease
- o Galactosemia
- o Glycogen storage disease
- o Hereditary fructose intolerance
- Patients taking any of the following:
 - o Cinnamon as a dietary supplement
 - o Daily oral steroids
 - o Warfarin
 - o Hypoglycemic medication
 - o Weight loss medication
 - o Digoxin, lithium, phenytoin, and theophylline (due to their narrow therapeutic index)
- Patients who are pregnant or breast feeding
- Patients with a known allergy to cinnamon
- Patients with a known allergy to wheat

3.6.8. Instrumentation: N/A

4.0. Human Subject Protection:

4.1. Recruitment:

All potentially eligible patients will be offered an opportunity to participate. Primary Care Managers (PCMs) who are not part of the research team will be informed about the study and provided information on the inclusion/exclusion criteria. PCM referrals and posted advertisements will be utilized for recruiting subjects to the study. Some patients may be patients of the PI or AI, however, they will have the study staff recruit their patients to prevent any misconception of coercion or undue influence. If a potential subject is identified by the treating PCM and is interested in obtaining more information about the study, the patient will either be provided a contact number to the Research Staff, the Research Staff will be given the potential subject's contact information by the PCM with the patient's oral or written authorization, or the PCM will come and get the Research Staff to speak with the patient directly. Lifestyle Intervention instructors will also provide referrals with the patient's oral or written authorization. We will also utilize the Marquees on base (the marquee will state: Pre-Diabetic, Contact (insert contact) for Cinnamon Trial, (insert phone number) for recruitment.

We are requesting a HIPAA Waiver so we are able to review the AHLTA schedule for potential participants. The data collected will only be used for recruiting and will be destroyed after contact with individual patients has been made. The clinical research coordinator will review the schedules of clinicians to find eligible patients within their schedule. The coordinator will proceed to inform the clinician of any possibly eligible subjects for the study. Each participating clinic will mail their pre-diabetic patients a letter informing them of the Cinnamon trial, and giving them the opportunity to participate or opt out. The mailing of these letters will be tasked to a study team member at the study site. We are also requesting to obtain a list from the Disease Management nurse on behalf of Family Medicine and Family Health Clinics. This list will be used to mail out letters to potential participants to increase recruitment

4.2. Consent Processes:

Informed consent and HIPAA authorization will be sought in advance from each prospective subject. Informed consent will be appropriately documented. [32 CFR 219.117] After discussion with the Investigator, the subject will be given the opportunity to consent. The Investigator will provide a written copy of the consent form and allow the subject to read it, review it with the subjects, and answer questions. The subject may decline to consent, and no pressure will be applied. If the subject consents, the proper signatures will be obtained, and a copy will be given to the subject.

4.3 Participation Compensation: Subjects will not be paid for participation in this study.

4.4. Assent Process: N/A

4.5. Benefits:

The benefits to the subjects may include lower hemoglobin A1c levels and improvement of long-term health by decreasing the risk of developing diabetes.

4.6. Risks:

Risks to the subject are minimal as the subjects have been diagnosed with pre-diabetes and will have to be treated regardless if they participate in this study or not. There are no known risks associated with water-soluble cinnamon, as it is a compound granted GRAS (Generally Recognized as Safe) status by the United States Food and Drug Administration. Potential risks include the inadvertent disclosure of personal health information and a potential for a cinnamon allergy that is not already known by the subject. The risks associated with the blood draw include bleeding, feeling light-headed, and bruising at the blood draw site and infection. Risks and side effects related to the water-soluble cinnamon extract include those, which are:

Less likely and not serious:

- **Hypoglycemia (low blood sugar):**
 - Heart palpitations (abnormal heart beats either fast or slow)
 - Tremors (involuntary muscle movement)
 - Hunger
 - Sweating

*If a subject experiences any of these symptoms, they are instructed to eat 15-20 grams of sugar [for example glucose (sugar) tablets], a glass of juice or other snack containing sugar, and then eat some carbohydrates (for example a small meal or cracker with peanut butter).

Less Likely and serious

- **Cinnamon and Wheat Bran:** There may be a risk that the subject has an allergy to cinnamon and wheat bran that they are not aware of currently. The signs and symptoms of an allergic reaction include:
 - o Shortness of breath
 - o Hives (itchy rash)
 - o Runny nose
 - o Watery eyes
 - o Sore eyes
 - o Asthma
 - o Lip swelling
 - o Tongue swelling
 - o Nausea
 - o Brochospasm (a bronchial spasm is a sudden constriction of the muscles in the walls of the bronchioles)
 - o Anaphylaxis (whole-body allergic reaction that has the following signs and symptoms):
 - Abdominal pain or cramping
 - Abnormal (high-pitched) breathing sounds
 - Anxiety
 - Confusion
 - Cough
 - Diarrhea
 - Difficulty breathing
 - Difficulty swallowing
 - Fainting, light-headedness, dizziness
 - Hives
 - Itchiness
 - Nasal congestion
 - Nausea, vomiting
 - Palpitations
 - Skin redness
 - Slurred speech
 - Wheezing

*If the subject experiences any of these symptoms, they are instructed to stop taking the study medication and seek urgent medical treatment.

Rare and serious

- **RAND-36 Health Questionnaire:** Risks and side effects related to the RAND-36 item Health Questionnaire include those which are:
 - o There is a risk (although rare) that the questionnaire may identify a subject as at risk for a mental health condition and result in a referral to mental health. Occasionally a person diagnosed with a mental health condition may be disqualified from active duty and a Medical Examination Board (MEB) referral.

4.7. Costs: There will be no additional costs to subjects for their participation in this research study.

4.8. Safeguards for Protecting Information:

How will coded or identifiable data/specimens be stored?	
---	--

[X]	Paper data, including completed consent forms	The research consents and HIPAA Authorization Documents will be stored in a locked cabinet in a locked room with restricted access.
[X]	Electronic data	Medical records will be annotated to reflect the subject's participation in a research study. All coded, de-identified research data will be electronically stored separately from the Master Key of identifiable patient demographics and PHI/PII.
[X]	Long-term storage (following completion of the study and inactivation of IRB approval)	The research data will be coded and any links to identifiable data will be destroyed (an approved shredding bin) as soon as possible or no later than at the closure of the study, with the exception of those study subjects that consent to place their de-identified research data into the "Nellis Diabetes Research Data Repository (FWH20110136H) for future research. The anonymized research data will not be utilized for further research activity beyond the protocol stipulations without additional IRB approval. All de-identified research data will be maintained for 3 years following study closure.

4.9. Safeguards for Protecting Subjects:

The Principal Investigator will be responsible for the protocol safety monitoring. The PI will make study documents (e.g., consent forms, data pulls) and pertinent hospital or clinical records readily available for inspection by the local IRB and over sight staff for confirmation of the study data. Integrity Nutraceuticals, Inc. will not have access to subjects' medical records.

4.9.1. Minimizing Risks:

Risks in this study are minimal and only relate to a blood draw and water-soluble cinnamon extract. Subjects will have access to study personnel should they have any issues. If there are any issues, they will be immediately reported to one of the Investigators and an applicable medical evaluation will be initiated. There is also a risk of inadvertent breach of confidentiality.

4.9.2. Vulnerable Populations: No vulnerable populations will be recruited.

4.9.3. Clinical Care:

If a subject experiences any injury, adverse event, or unexpected clinical finding, a PI, AI, or Primary Care Manager will be available to assess the subject and initiate proper clinical care.

4.9.4. Injury Compensation: Subjects will not be compensated for injuries.

4.9.5. Data Safety Monitoring:

The trial will be conducted in compliance with this protocol, International Conference on Harmonization (ICH) Guidelines for Good Clinical Practice (GCP), and any applicable national and international regulatory requirements. The Principal and Associate Investigators will be monitoring all aspects of the study in accordance with the appropriate regulations and will have regular meetings with periodic quality control of data documentation and collection. The objectives of the monitoring meetings will be:

- 1) To verify the prompt reporting of all data points, including reporting SAE's and checking availability of signed informed consent,
- 2) To compare individual subject records, data pulls and/or the study source documents/case report forms (supporting data, laboratory specimen records and medical records to include physician progress notes, nurses' notes, subjects' hospital charts),
- 3) To ensure protection of study subjects, compliance with the protocol, and accuracy and completeness of records.

[name], DO, Capt (Primary) and [name], Capt (alternate) will be the research monitors assigned to this study.

The PI will make study documents (e.g., consent forms, data pulls) and pertinent hospital or clinical records readily available for inspection by the local IRB and over sight staff for confirmation of the study data.

5.0. Alternatives: The alternative is not to participate in this study.

6.0. Data Analysis:

6.1. Outcome Measures:

We will be assessing the effect of 1 gram (2-500 mg capsules) of water-soluble cinnamon extract (Cinnulin PF) on pre-diabetic subjects and obtaining hemoglobin A1c, lipid panel, height, weight, and waist circumference measurements (in inches).

6.2. Sample size estimation/power analysis:

A priori power for H₀₁ was assessed using G*Power Version 3.0.10¹. The results indicate 214 subjects per group with 8 repeated measures for a total sample size of 3424 will achieve a power of approximately 0.99 to detect a small effect size of 0.10 at α = 0.0004.

A priori power for H₀₂ was assessed using the method described by Glantz² to calculate sample size for a two-sample log-rank test to detect differences in the time to event. Based on this design, it will require a minimum of 214 subjects per group to detect a difference between a 17.5% conversion in the Placebo + lifestyle and an 11.5% conversion in the Cinnulin + lifestyle group at α = 0.05 (one-sided) and power of 0.80.

We are enrolling 557 subjects total, for an expected 428 completing the study. We estimate 129 subjects' will either withdraw consent or drop out of the study.

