2. Type 2 diabetes conversion: Yes/No

Other Variables of Interest among Subjects

1. Subject Demographics
 - a. Age (years)
 - b. Marital Status (single versus married)
 - c. Gender
 - d. Race/Ethnicity (African American, European American, or Hispanic, 2 parameters)
 - e. Specialty codes (categorized into office work, logistics, or combat specialties, 2 parameters)
 - f. Military Grade (Officer grades categorized into company, field or higher ranks; enlisted into E1 – E6 or E7 – E9).

Sample Size Estimation and Power Analysis: A priori power for H_01 was assessed using G*Power Version 3.0.10³. The results shown below indicate 214 subjects per group with 8 repeated measures for a total sample size of 3424 will achieve a power of approximately 0.99 to detect a small effect size of 0.10 at $\alpha = 0.0004$.

Input:	Effect size f	=	0.1
	β/α ratio	=	4
	Total sample size	=	3424
	Number of groups	=	2
	Repetitions	=	8
	Corr among rep measures	=	0.8
Output:	Noncentrality parameter λ	=	41.503030
	Critical F	=	12.389225
	Numerator df	=	1.000000
	Denominator df	=	3422
	α err prob	=	0.000437447
	β err prob	=	0.00174979
	Power (1- β err prob)	=	0.998250

[figure not shown]

Figure 1. rANOVA Power, $\beta = 0.002$, $\alpha = 0.0004$, 214 subjects per group

Post hoc analyses to evaluate differences within clinically significant time intervals will be tested with one-tailed t-tests for independent samples. The power analysis, using G*Power Version 3.0.10⁴, is shown below and shows 214 subjects per group will achieve a power of approximately 0.85 to detect a small effect size of 0.20. To lessen the probability of a false negative, a β/α ratio of 1 was employed.

t tests - Means: Difference between two independent means (two groups)

Analysis:	Compromise: Compute implied α & power		
Input:	Tail(s)	=	One
	Effect size d	=	0.2
	β/α ratio	=	1
	Sample size group 1	=	214
	Sample size group 2	=	214
Output:	Noncentrality parameter δ	=	2.068816
	Critical t	=	1.035015
	Df	=	426
	α err prob	=	0.150624
	β err prob	=	0.150624
	Power (1- β err prob)	=	0.849376

³ Faul F, Erdfelder E, Lang A-G, Buchner A. G*Power 3: A flexible statistical power analysis program for the social, behavioral, and biomedical sciences. *Behavior Research Methods*. 2007; 39 (2): 175-191.

⁴ Ibid.

[figure not shown]

Figure 2. *t*-test Power, $\beta = 0.15$, $\alpha = 0.15$, 214 subjects per group

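### The only significance level attached to H01 (0.0004, with power 0.99) is an output of a power run that entered 3424 measurements as subjects; with 428 subjects, power at that level is about 0.10

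*Combined protocol and SAP*

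**What the plan says.** Section 6.2, repeated in the SAP at 6.3 (Sample Size Estimation and Power Analysis), gives the H01 power statement. The sample is described as "214 subjects per group with 8 repeated measures for a total sample size of 3424". The claim made for a sample of that size is that it "will achieve a power of approximately 0.99 to detect a small effect size of 0.10 at α = 0.0004". Both places describe this as a priori power.

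The G*Power table in 6.3 lists among its inputs "β/α ratio = 4", "Total sample size = 3424", 8 repetitions and "Corr among rep measures = 0.8". Among its outputs are "Noncentrality parameter λ = 41.503030", critical F 12.389225, denominator df 3422, alpha 0.000437447, beta 0.00174979 and power 0.998250.

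A companion t-test run for the post hoc comparisons is headed "Compromise: Compute implied α & power". It uses a ratio of 1 and 214 per group, and returns alpha = beta = 0.150624.

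On subject numbers, 6.2 says: "We are enrolling 557 subjects total, for an expected 428 completing the study".

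Under Hypothesis Testing in 6.3, H01 is assigned to a repeated-measures ANOVA with no significance level. Post hoc contrasts follow only if H01 is rejected. Bonferroni or Holm is to be applied if multiple univariate tests are used, but the level to be corrected is not named. H02, by contrast, has a stated one-sided 0.05 in its sample-size text.

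**The concern.** Two things look wrong in the H01 power statement, and they compound.

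First, alpha is not an input. A run that takes a β/α ratio and returns alpha gives whatever level balances the two errors for the N entered, so alpha moves when N moves.

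Second, the N entered is a count of measurements. The formula already credits the 8 repeats through the repetitions and correlation inputs, so multiplying N by 8 as well credits them twice.

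H01 covers glucose, HbA1c, lipids and waist circumference, and its rejection is the gate to the post hoc contrasts. If the plan's only level for that test comes from a mis-specified run, a reader cannot tell what p-value rejects H01, and the power of 0.99 gives false assurance about these outcomes.

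**Working it through.** **Inputs.** From the 6.3 table: f = 0.1, 2 groups, m = 8 repetitions, ρ = 0.8, β/α ratio = 4, N = 3424. From 6.2: 428 completers (214 per group), 557 enrolled.

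**Formulas** (between-groups effect in a repeated-measures ANOVA):
- λ = f² × N × m / (1 + (m − 1)ρ), with df = (1, N − 2).
- The ratio run finds the critical F at which β (the noncentral F probability below it) equals 4 × α (the central F upper tail).

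**Step 1: reproduce the plan's figures.**
- 214 × 2 × 8 = 3424, and 3424 − 2 = 3422, the printed denominator df.
- λ = 0.01 × 3424 × 8 / (1 + 7 × 0.8) = 273.92 / 6.6 = 41.503.
- Solving β = 4α gives F = 12.389225, α = 0.00043745, β = 0.00174979 and power 0.998250.

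Every printed output is matched, and the printed β is four times the printed α. The H01 run is therefore of the compromise type, although that word is printed only above the t-test block. The t-test block also reproduces (δ = 2.068816, critical t = 1.035015, α = β = 0.150624).

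**Step 2: same run with subjects as N.**
- λ = 0.01 × 428 × 8 / 6.6 = 34.24 / 6.6 = 5.188, one eighth of the printed value.
- Solving β = 4α with df (1, 426) gives F = 3.147, α = 0.0768, β = 0.307 and power 0.693.
- The alpha is about 0.0768 / 0.000437 ≈ 176 times the printed one.

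**Step 3: power on 428 subjects with alpha fixed** (λ = 5.188, df 1 and 426).

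| Alpha | Critical F | Power for f = 0.10 |
|---|---|---|
| 0.0004 | 12.733 | 0.100 |
| 0.000437 | 12.561 | 0.105 |
| 0.05/7 = 0.00714 | 7.307 | 0.336 |
| 0.05 | 3.863 | 0.623 |

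**Step 4: the observed difference needed to reject.** With SE = √(6.6/8) × √(2/214) = 0.908 × 0.0967 = 0.0878 SD:
- at 0.000437: √12.561 × 0.0878 = 3.544 × 0.0878 = 0.31 SD;
- at two-sided 0.05: √3.863 × 0.0878 = 1.966 × 0.0878 = 0.17 SD.

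For two equal groups f = 0.1 is a difference of 0.2 SD. At the printed alpha the observed difference must therefore be about one and a half times the true difference assumed.

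**Step 5: sensitivity.**
- Ratio run with N = 557: α = 0.060, power 0.76.
- Ratio run with N = 428 and ρ from 0.5 to 0.9: α from 0.052 to 0.083.
- Ratio run with N = 428 and 4, 5 or 9 repeats: α = 0.079, 0.078 or 0.077.
- Power at α = 0.0004 with N = 428: 0.21 at ρ = 0.5 (λ = 34.24/4.5 = 7.61) and 0.08 at ρ = 0.9 (λ = 34.24/7.3 = 4.69).
- Power at α = 0.0004 with N = 557 and ρ = 0.8: 0.17 (λ = 44.56/6.6 = 6.75).

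No subject-level N tested brings alpha near 0.0004 in the ratio run, or power near 0.99 at that alpha.

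**The case against.** The best defence is that 0.0004 is a power-section number and not a decision rule. It appears only in the sample-size text, the output table and a figure caption. The testing step never adopts it. Nor is choosing a β/α ratio an error in itself: it is a deliberate if unusual way to balance the two errors, and for the t-tests the SAP explains its choice. Describing the power as a priori can simply mean that it was computed before the data, and the inputs and outputs are openly printed. Finally, the first study goal is time to diabetes, and the 428 comes from the H02 calculation, so enrolment and the H02 test are unaffected.

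All of that stands, and it limits the point. It does not remove it. If 0.0004 is not the level for H01, then none is stated. The stated pairing of 0.99 power with 0.0004 is wrong on either reading.

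A reader might go further and infer that any p-value between 0.0004 and 0.077 has no defined verdict. The documents do not support that. The value 0.077 is a recalculation and appears nowhere in the plan, so it bounds nothing. If 0.0004 binds, p = 0.01 does not reject; if it does not bind, the gap covers every p-value. Nor do the documents show an intention to pick a level after seeing the data, or adopt 0.15 as a decision level.

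**Conclusion.** The point holds as a defect in the stated alpha/power pair and an omission in the testing step. The plan's only level for H01 is the output of a run whose N is eight times the number of subjects. On 428 subjects the same run gives alpha 0.077 and power 0.69. At the printed 0.0004, power is about 0.10 against the stated 0.99. Either the H01 test is run at a level where it has about 10% power, or it has no pre-specified level although it gates the post hoc contrasts.

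These sizes rest on the SAP's own f = 0.10, 8 repeats and correlation 0.8, and on 428 analysed subjects. Varying the correlation from 0.5 to 0.9, or using all 557 at correlation 0.8, leaves power at 0.0004 between 0.08 and 0.21. The conclusion concerns H01 only and says nothing about the H02 sample size.

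**What to change.** 1. In 6.2 and 6.3, withdraw the 0.0004/0.99 statement and the ratio-based run behind it.
2. In the H01 testing step of 6.3, state one fixed alpha and its sidedness, chosen independently of N (for example two-sided 0.05), and the multiplicity rule across the H01 outcomes.
3. Re-run the power calculation with alpha as an input and N = 428 subjects. Print power at the level each outcome will actually be tested at: 0.62 if each is tested at two-sided 0.05, or about 0.34 at 0.05/7 if 0.05 is split equally over the seven listed variables (glucose, HbA1c, four lipids, waist). Quoting 0.62 while splitting the alpha would overstate power.
4. State that the 0.15 from the t-test compromise run is not a decision level.

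The cost is SAP wording and one re-run of the software. The printed power will look less favourable. No extra patients or data are needed.
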